6.1.1.2 Transplant-Related Mortality up to 180 Days

A transplant-related death is defined as any death without prior diagnosis of relapse. Time to transplant-related death up to 180 days is calculated as date of transplant-related death minus date of randomization plus 1. Competing risk is the diagnosis of relapse up to 180 days with

time to diagnosis of relapse calculated as date of diagnosis of relapse minus date of randomization plus 1.

For a subject without a transplant-related death or diagnosis of relapse up to 180 days, the time will be censored at the earliest of the days below:

- at Study Day 180 if the subject is known to be alive at Study Day 180
- at day of last contact if subject gets lost to follow-up prior to Study Day 180.

6.1.2 Secondary Efficacy

6.1.2.1 Overall Survival up to 180 Days

The key secondary efficacy endpoint is OS up to 180 days.

OS up to 180 days will be calculated as date of death (from any cause) minus date of randomization plus 1. It will be censored

- at Study Day 180 if the subject is known to be alive at Study Day 180
- at day of last contact if subject gets lost to follow-up prior to Study Day 180.

6.1.2.2 Change from Baseline in Stages of GvHD by Target Organ

Stages of GvHD, by target organ, will be evaluated at the visits presented in Table 19. These stages will be used to determine the change from baseline in stages of GvHD by target organ at Study Day 28.

6.1.2.3 Chronic Graft-versus Host Disease up to 180 Days

The presence of GvHD is to be assessed at each visit (Table 19). The date of occurrence of chronic GvHD in an individual subject is to be recorded.

Chronic GvHD not requiring systemic treatment is defined as:

1. Mild abnormalities involving a single site, with platelet count $>100,000$ and no steroid treatment at the onset of chronic GvHD, which could include:
 - Oral abnormalities consistent with chronic GvHD, a positive skin or lip biopsy, and no other manifestations of chronic GvHD.
 - Mild liver test abnormalities (alkaline phosphatase [ALP] $\leq 2 \times$ ULN, aspartate aminotransferase [AST] or alanine aminotransferase [ALT] $\leq 3 \times$ ULN and total bilirubin ≤ 1.6) with positive skin or lip biopsy, and no other manifestations of chronic GvHD.

- Less than 6 papulosquamous plaques, macular-papular or lichenoid rash involving <20% of BSA, dyspigmentation involving <20% BSA, or erythema involving <50% BSA, positive skin biopsy and no other manifestations of chronic GvHD.
 - Ocular sicca (Schirmer's test ≤ 5 mm with no more than minimal ocular symptoms), positive skin or lip biopsy, and no other manifestations of chronic GvHD.
 - Vaginal or vulvar abnormalities with positive biopsy, and no other manifestations of chronic GvHD.
2. Platelet count <100,000 or steroid treatment at the onset of chronic GvHD:
- Involvement of two or more organs with symptoms or signs of chronic GvHD, with biopsy.
 - Documentation of chronic GvHD in any organ.
 - $\geq 15\%$ baseline body weight loss not due to other causes, with biopsy documentation of chronic GvHD in any organ.
 - Skin involvement more extensive than defined for clinical limited chronic GvHD, confirmed by biopsy.
 - Scleroderma or morphea.
 - Onycholysis or onychodystrophy thought to represent chronic GvHD, with documentation of chronic GvHD in any organ.
 - Decreased range of motion in wrist or ankle extension due to fasciitis caused by chronic GvHD.
 - Contractures thought to represent chronic GvHD.
 - Oral involvement with functional impairment, refractory to topical treatment.
 - Vaginal involvement with functional impairment, refractory to topical treatment.
 - Bronchiolitis obliterans not due to other causes.
 - Positive liver biopsy or abnormal liver function tests not due to other causes with ALP $>2 \times$ ULN, AST or ALT $>3 \times$ ULN, or total bilirubin >1.6 , and documentation of chronic GvHD in any organ.
 - Positive upper or lower GI biopsy.
 - Fasciitis or serositis thought to represent chronic GvHD and not due to other causes.

Time to diagnosis of chronic GvHD up to 180 days is calculated as date of diagnosis of chronic GvHD minus date of randomization plus 1. Competing risk is death (if prior to Study
Confidential

Day 180 and prior to diagnosis of chronic GvHD) with time to death calculated as date of death minus date of randomization plus 1.

For a subject without a diagnosis of chronic GvHD or death up to 180 days, the time will be censored at the earliest of the days below:

- at Study Day 180 if the subject is known to be alive without diagnosis of chronic GvHD at Study Day 180
- at day of last contact if subject gets lost to follow-up prior to Study Day 180.

6.1.2.4 Cumulative Steroid Dose

The dose and route of steroids used will be reported at the visits presented in Table 19.

6.1.2.5 Relapse and Relapse-Related Mortality

Clinical relapse of the underlying malignancy will be recorded, as identified by standard procedures. This could include, but is not limited to, physical examination, assessment of symptoms, complete blood count, imaging assessments, and bone marrow biopsy/aspirate.

The identification of minimal residual disease should not be considered as a clinical relapse.

Time to relapse up to 180 days is calculated as date of relapse diagnosis minus date of randomization plus 1. Competing risk is death prior to diagnosis of relapse (if prior to Study Day 180) with time to death calculated as date of death minus date of randomization plus 1.

For a subject without a relapse diagnosis or death up to 180 days, the time will be censored at the earliest of the days below:

- at Study Day 180 if the subject is known to be alive without a relapse diagnosis at Study Day 180
- at day of last contact if subject gets lost to follow-up prior to Study Day 180.

A relapse-related death is defined as any death with prior diagnosis of relapse. Time to relapse-related death up to 180 days is calculated as date of relapse-related death minus date of randomization plus 1. Competing risk is death without prior diagnosis of relapse (if prior to Study Day 180) with time to death without prior diagnosis of relapse calculated as date of death minus date of randomization plus 1.

For subjects without a death up to 180 days it will be censored at the earliest of the days below:

- at Study Day 180 if the subject is known to be alive at Study Day 180
- at day of last contact if subject gets lost to follow-up prior to Study Day 180.

6.1.2.6 Change from Baseline in Karnofsky Performance Status

The Karnofsky Performance Status scale allows subjects to be classified according to their functional impairment.

The change from baseline in the Karnofsky Performance Status scale will be derived for the timepoints noted in Table 19.

A copy of the Karnofsky Performance Status scale is provided in Appendix 2 (Section 12.2).

6.1.3 Exploratory Efficacy

Exploratory efficacy include:

- Quality of life (QoL) based on the SF36 assessed at the visits noted in Table 19.
- Duration of response up to Study Day 90 (calculated from the date at which PR or CR is documented).
- Overall response by standard-risk and high-risk GvHD ([MacMillan et al., 2015](#)).

6.2 Safety

6.2.1 Adverse Events

The investigator is responsible for recording all AEs observed in during the study, from the time that informed consent is signed through Study Day 58 or up to 30 days after the last dose of study treatment, whichever is later; at that time, any ongoing adverse drug reaction (ADR) and/or SAE event are to be followed until resolution (up to Study Day 180). AEs will be recorded in the subject's eCRF.

Second malignancies and deaths will be recorded as SAEs through Study Day 180.

Information about all AEs, whether volunteered by the subject, discovered by investigator questioning, or detected through physical examination, laboratory test or other means, will be collected and recorded on the AE page of the eCRF and followed as appropriate.

Diagnostic and therapeutic non-invasive and invasive (i.e. surgical) procedures will not be reported as AEs. However, the medical condition for which the procedure was performed must be reported if it meets the definition of an AE, unless it is a pre-existing (prior to stem cell transplantation (SCT)/chemotherapy) condition.

Underlying disease being studied (GvHD) will not be reported as an AE, unless is deemed as more severe than expected.

Medical conditions/diseases present before starting study drug are only considered AEs if they worsen after starting study treatment.

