4.0 INVESTIGATIONAL PLAN

4.1 Summary of Study Design

This will be a prospective, multicenter, randomized, open-label, phase II/III clinical study in which subjects will be randomly assigned in a 1:1 ratio to receive BEGEDINA treatment or the best conventional treatment. Randomization will be stratified by the baseline GvHD severity grade to either Grade B GvHD or Grade C/D GvHD.

The study will be conducted at approximately 30 bone marrow transplantation units in Europe, US and Canada. It is planned to enroll 184 subjects with steroid-resistant acute GvHD. The subjects will be randomized (1:1) to one of two treatment arms:

- BEGEDINA IV at a dose of 2.7 mg/m²/day for 5 consecutive days from Study Day 1 through to Study Day 5, and on Study Days 10, 14, 17, 21, 24, and 28.*
- Conventional second-line treatment: a single treatment (agent), chosen at the discretion of the investigator (physician's best choice) and based on the clinical conditions of the individual subject. The treatment will be given as per prescribing instructions (and/or standard practice of the center).

Patients in both arms are to continue (or initiate) baseline therapy of methylprednisolone (or other steroid equivalent) and calcineurin inhibitor (see Section 5.7.2.4.1).

*Please note: the term "Study Day" as used throughout the protocol is used in relation to the day that randomized study treatment started and not in relation to the day of transplant.

All subjects will undergo a screening visit to assess for eligibility and for screening assessments; this visit must take place within 2 days of Baseline. After screening, subjects will undergo randomization and the baseline visit, which is also the first day of study treatment (Study Day 1) (i.e., subjects must commence study treatment within two days of meeting eligibility). Study visits will be conducted at various timepoints (Table 19) through Study Day 180.

The experimental phase of the study will end for each subject on Study Day 180. An extended, long-term, observational follow-up is also planned in order to capture survival, response/relapse, glucose metabolism, health outcomes and safety data out to Study Day 180. Thus, the expected duration for an individual subject who completes the study according to the protocol will be approximately 6 months, including screening and 180-day follow-up.

Table 19 Schedule of Events

Study Day Visit Windows Assessments	Screening ^a	Experimental Phase																		Early Withdrawal	

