5.5 Selection and Timing of Dose for Each Subject

All subjects randomized to the BEGEDINA treatment arm will receive 2.7 mg/m²/day IV for 5 consecutive days (Study Days 1, 2, 3, 4, 5) and on Study Days 10, 14, 17, 21, 24 and 28.

All subjects randomized to the conventional treatment arm will receive the treatment according to the relevant prescribing instructions (and/or standard practice of the center).

The rationale for the BEGEDINA dosing regimen and the choice of conventional treatment are discussed in Sections 4.3.1 and 4.3.2, respectively.

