5.9 Management of a GvHD Flare

An acute GvHD flare is defined as worsening of acute GvHD in any organ by at least one stage beyond Study Day +28, subsequent to achieving PR or CR to Initial Therapy.

Subjects who have been randomized to the BEGEDINA arm and who have a GvHD flare after Study Day 28 and before Study Day 90 may receive additional BEGEDINA treatment as follows:

- Subjects must have had documented CR or PR at Day+28.
- Treatment consists of the Initial Therapy Plan (i.e. 5 consecutive days plus days 10, 14, 17, 21, 24 and 28 from the start of the flare) as in the Schedule of Events (Table 19).
- Subjects are recommended to remain in the hospital for treatment of flare, however, at the discretion of the investigator, may be treated in day-hospital facilities; subjects must be monitored (under hospital observation through 2 hours after the start of the infusion) and as per the Schedule of Events (Table 19), with special attention to risk of infusion related reactions (5.1.1.1, 6.2.1.5).[?]
- If a subject has begun other steroid-resistant acute GvHD therapy within the active study treatment period (up to and including Day 28), they would not be eligible to receive further BEGEDINA therapy.

Subjects in the conventional treatment arm may continue or restart therapy as per investigator judgment.

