8.3.7 Safety Analyses

For each study treatment, numbers of AEs and incidence rates will be tabulated by MedDRA system organ class and preferred term. An event that occurred one or more times on the date of, or subsequent to, randomization will contribute one observation to the numerator of the incidence rate. The denominator of the rate will comprise all randomized subjects exposed to the study treatment. If the intensity or seriousness of the AE changes, then the overall intensity or seriousness will be the maximum intensity or seriousness of the multiple occurrences.

Serious adverse events, AEs leading to death and AEs leading to withdrawal of subjects will be tabulated for each treatment group. Commonly occurring AEs, i.e. those which occur in 5% or more of the subjects in either treatment group, will be summarized using descriptive statistics.

Descriptive statistics will be used to present physical examination results, weight, BMI, vital signs measurements; clinical laboratory test results; and ECG results – for both raw values and change from baseline. Shift tables will be presented for selected tests.

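### Crude AE percentages can compare unequal recording windows, because recording ends 30 days after a last dose that has no fixed day in the conventional arm

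*Combined protocol and SAP*

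**What the plan says.** **Recording period.** Section 6.2.1 has the investigator record AEs from the time consent is "signed through Study Day 58 or up to 30 days after the last dose of study treatment, whichever is later". Section 6.2.1.2 repeats this, and the AE footnote to Table 19 applies it to both arms. Deaths and second malignancies are the exception: they are recorded to Day 180.

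**Dosing that drives the period.** BEGEDINA is scheduled to end on Day 28 (Section 5.1.1). For the conventional agent, Section 4.1 says "The treatment will be given as per prescribing instructions (and/or standard practice of the center", and Section 5.5 says "All subjects randomized to the conventional treatment arm will receive the treatment according to the relevant prescribing instructions". Neither gives a last day. Section 5.9 adds "Subjects in the conventional treatment arm may continue or restart therapy as per investigator judgment".

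**Flare courses.** Under Section 5.9, BEGEDINA subjects who "have a GvHD flare after Study Day 28 and before Study Day 90 may receive additional BEGEDINA treatment as follows" may get a second full course. The same section also uses the phrase "within the active study treatment period (up to and including Day 28". It does not say whether a flare dose counts as study treatment for the 30-day rule.

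**Analysis.** Section 8.3.7 states: "An event that occurred one or more times on the date of, or subsequent to, randomization will contribute one observation to the numerator". It then says: "The denominator of the rate will comprise all randomized subjects exposed to the study treatment". It names no end day and no person-time. Section 8.3.2 summarizes treatment duration separately. Section 8.0 leaves further detail to a SAP that is not among the documents.

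**The concern.** Comparing the safety and tolerability of the two arms is a stated objective (Section 3.1.3). A crude percentage compares arms fairly only if subjects in both are recorded for similar lengths of time. Here the length follows from how long treatment lasts, and that differs by arm by design. An arm recorded for longer collects more first events even if the drugs are equally toxic.

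The most exposed rows are the less frequent preferred terms and SAEs other than deaths and second malignancies. Rows near 100% have little room to move, and every subject in both earlier BEGEDINA studies had at least one AE. The listing of AEs that reach 5% in either arm is also sensitive, because window length can decide whether a term appears.

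For SAEs the protocol pulls two ways. Section 6.2.1.2 ends recording, serious events included, at the dose-linked date. Section 6.2.1.3 asks for any SAE arising during the study.

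**Working it through.** **Window ends.** The rule is min(180, max(58, last dose day + 30)).

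- BEGEDINA, scheduled course: 28 + 30 = Day 58, which reproduces the protocol's figure.
- Conventional agent: last dose by Day 28 gives Day 58; Day 60 gives Day 90; Day 90 gives Day 120; Day 150 or later gives Day 180.
- BEGEDINA flare course, if it restarts the clock: a start on Day 29, 60 or 89 puts the last dose (start + 27) on Day 56, 87 or 116 and the window end on Day 86, 117 or 146.

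**Inputs from the protocol.** TRM by Day 180 of 30% (BEGEDINA) and 50% (control), and response of 75% and 50%, from Section 8.1. A 41% flare figure from Section 2.1.2.2.2, quoted there for subjects treated with another agent.

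**Assumed, not in the documents.** An AE with 30% incidence by Day 58 in the absence of death; the same hazard in both arms; half or a quarter of controls dosed to Day 90; flares on Day 60, all retreated; the 41% applied to responders in both arms.

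**Formulas.**

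- AE hazard h = -ln(0.70)/58 = 0.00615 per day to Day 58, then k·h with k = 1, 0.5 or 0.25.
- Death hazard d = -ln(0.70)/180 = 0.00198 (BEGEDINA) and -ln(0.50)/180 = 0.00385 (control).
- inc(58) = h/(h+d) × [1 - exp(-58(h+d))].
- For w > 58, add exp(-58(h+d)) × kh/(kh+d) × [1 - exp(-(kh+d)(w-58))].

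**Common Day 58 window.** BEGEDINA 28.44%, control 27.06%: a gap of -1.4 points from mortality alone. The first-event rate is equal in both arms, at 0.00615 × 30.4 = 0.187 per 30.4 days at risk.

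**Scenarios.**

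1. Flare courses do not extend recording; a fraction f of controls is dosed to Day 90. Control = (1-f)·inc(58) + f·inc(120). For f = 0.5 and k = 1: 0.5 × 27.06 + 0.5 × 42.97 = 35.0%.
2. Flare courses extend recording in both arms, with no other late control dosing. Shares are 0.75 × 0.41 = 0.3075 and 0.50 × 0.41 = 0.205. For k = 1, BEGEDINA = 0.6925 × 28.44 + 0.3075 × 46.42 = 34.0%; control = 0.795 × 27.06 + 0.205 × 42.41 = 30.2%.
3. Both mechanisms, f = 0.5. BEGEDINA as in 2; control = 0.5·inc(120) + 0.5 × its value in 2.

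| BEGEDINA vs control (%) | k = 1 | k = 0.5 | k = 0.25 |
|---|---|---|---|
| 1, f = 0.5, no deaths | 30.0 vs 41.1 | 30.0 vs 36.1 | 30.0 vs 33.2 |
| 1, f = 0.5, with TRM | 28.4 vs 35.0 | 28.4 vs 31.4 | 28.4 vs 29.3 |
| 1, f = 0.25, with TRM | 28.4 vs 31.0 | 28.4 vs 29.2 | 28.4 vs 28.2 |
| 2, with TRM | 34.0 vs 30.2 | 31.4 vs 28.8 | 30.0 vs 28.0 |
| 3, with TRM | 34.0 vs 36.6 | 31.4 vs 32.3 | 30.0 vs 29.8 |

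With mortality included, control minus BEGEDINA runs from -3.8 (scenario 2, k = 1) to +6.6 (scenario 1, f = 0.5, k = 1).

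**Two checks.** At 95% incidence by Day 58, with no deaths, f = 0.5 and k = 1, the result is 95.0% vs 97.4%, a gap of 2.4 points. For the 5% listing, with constant hazard and no deaths, a term with a 58-day incidence of 1 - 0.95^(58/120) = 2.45% reaches 5% in subjects recorded to Day 120.

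**The case against.** Five points can be made for the plan.

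- **The SAP may set a cut-off.** Section 8 is only the basis for the SAP, and AE cut-offs often sit there. This stands as a limit: the point concerns the protocol text, and a SAP with a common window would leave only the clarifications.
- **The largest gap uses the less natural reading of the flare rule.** A flare course is further BEGEDINA on the original schedule, so ordinarily it would move the last-dose date. The phrase that ties active treatment to Day 28 belongs to a rule on eligibility for retreatment. This is fair. With both mechanisms at work (scenario 3), the gap is +2.6, +0.8 and -0.2 points. But offsetting windows would be luck, and the protocol does not state the reading.
- **No direction is shown, and the drivers are assumed.** True. If control agents stop by Day 28 and flares are few, both windows close at Day 58 and nothing is distorted.
- **Last dose plus 30 days is a recognizable as-treated convention.** Extra control events may partly be real toxicity of a longer regimen. This is a good reason to keep the full-window tables. They still cannot separate greater toxicity from longer recording.
- **Safety is descriptive and exposure is tabulated.** No test or decision rule uses these percentages, which limits the consequence. But readers cannot correct an AE percentage from a separate duration table.

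**Conclusion.** The concern holds for the protocol as written. AE recording is tied to the last dose, one arm has no fixed last dose, and the planned percentage takes no account of recording time.

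The distortion can favor either arm. Under the assumptions above it ranges from negligible to several points for an AE of moderate frequency, and it shrinks when late hazards fall or few controls are treated for long. No single figure should be read as a prediction, because the documents give no control treatment duration, no late AE hazard and no flare rate for this trial. Deaths and second malignancies are not affected.

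This should be changed because the remedy is cheap and the comparison is a stated objective. Confidence is medium, since the SAP was not seen.

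**What to change.** In Section 8.3.7 and the SAP:

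- Keep the full-window AE tables as planned.
- Base the between-arm comparison of AEs, and of SAEs other than deaths and second malignancies, on randomization to Day 58, the minimum planned recording period in both arms.
- In that window, report first-event rates per patient-time at risk, or cumulative incidence with death as a competing event. A common cut-off alone does not remove the effect of unequal mortality.
- Tabulate later events separately with their time at risk. Leave deaths and second malignancies to Day 180.

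In Sections 5.9 and 6.2.1, state whether a flare course restarts the 30-day recording period. Reconcile the SAE end date between Sections 6.2.1.2 and 6.2.1.3. Neither edit changes a treatment rule.

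**Cost.** SAP and table-shell wording, two clarifying sentences and a few extra tables; AE, dosing and death dates are already collected. The drawback is that late toxicity of long control regimens, and of second BEGEDINA courses, falls outside the common-window comparison. That is why the full-window and late-event tables must stay.

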6.2.1.1 Definitions of AEs, Severity, Relationship (Causality), Action Taken and Outcome

Adverse events will be classified and their severity will be graded using the National Cancer Institute (NCI) CTCAE version 4.0 (http://evs.nci.nih.gov/ftp1/CTCAE/CTCAE_4.03_2010-06-14_QuickReference_5x7.pdf).

Each AE is to be evaluated by the investigator for duration, severity, seriousness and causal relationship to the investigational drug. The action taken and the outcome must also be recorded.

NCI CTCAE Grade 3-4 laboratory abnormalities are to be recorded as AEs independent of associated signs or symptoms. The associated signs and symptoms should be considered as additional event terms and graded according to their own criteria.

Definitions of AEs

An AE is any untoward medical occurrence in a subject or clinical investigation subject administered a pharmaceutical product, medical treatment or procedure and which does not necessarily have to have a causal relationship with this treatment. An AE can therefore be any unfavorable and unintended sign (including an abnormal laboratory finding), symptom or disease temporally associated with the use of a medicinal product, medical treatment or procedure whether or not considered related.

An SAE, experience or reaction, is any untoward medical occurrence or effect (whether or not considered to be related to study drug) that at any dose meets one or more of the Seriousness (or Gravity) criteria listed below:

- Results in death.
- Is life-threatening (the subject is at a risk of death at the time of the event; it does not refer to an event which hypothetically might have caused death if it were more severe).
- Requires inpatient hospitalization or prolongation of existing hospitalization: Hospital admissions and/or surgical operations planned before or during a study are not considered AEs if the illness or disease existed before the subject was enrolled in the study, provided that it did not deteriorate in an unexpected way during the study.
- Results in persistent or significant disability/incapacity.

- Is a congenital abnormality/birth defect.
- Other: Medically significant events, which do not meet any of the criteria above, but may be considered serious when, based on medical judgment, they may jeopardize the subject or may require medical or surgical intervention to prevent one of the other serious outcomes listed in the definition above. Examples of such events include allergic bronchospasm requiring intensive treatment in an emergency room or at home, blood dyscrasias (e.g. neutropenia or anemia requiring blood transfusion, etc.) or convulsions that do not result in hospitalization, or the development of drug dependency or drug abuse.

An ADR is defined as all untoward and unintended responses to an IMP related to any dose administered.

An Unexpected ADR is defined as any adverse reaction, whose nature, severity or frequency is not consistent with the applicable product information specified in the IB. Adverse Drug Reactions which are unexpected and satisfy one of the seriousness criteria specified above, meet the definition of Suspected Unexpected Serious Adverse Reactions (SUSARs). In addition, the following events are expected following stem cell transplant and / or diagnosis of acute GvHD ([Copelan, 2006](#)) and as such should not be considered as ADRs, unless in the investigator's opinion there is at least a possible relationship with study drug:

febrile neutropenia, mucositis (nausea, vomiting, abdominal pain, diarrhea), veno-occlusive disease (also known as sinusoidal obstructive syndrome, with resulting hepatomegaly, fluid retention, ascites, renal or respiratory failure), transplantation related lung injury (with pneumonitis/pulmonary infiltrates, respiratory failure), transplantation related infections, recurrence of acute GvHD (with rash, jaundice, abdominal pain, diarrhea, bloody stool), chronic GvHD (with resulting bronchiolitis, malabsorption, cholestasis, hematocytopenia), relapse of underlying disease and secondary malignancies (including but not limited to the skin, oral mucosa, brain, thyroid and bone).

Severity

Adverse events will be classified and their severity will be graded using the NCI CTCAE version 4.0.

Relationship

The causal relationship between the study medication and the AE will be determined by the investigator according to the following criteria:

- Not related: The event or laboratory test abnormality is most likely produced by other factors such as the subject's clinical condition, intercurrent illness, or concomitant drugs, and does not follow a known response pattern to the study drug, or the temporal relationship of the event to study drug administration makes a causal relationship unlikely.
- Possibly related: The event or laboratory test abnormality follows a reasonable temporal sequence from the time of drug administration, and/or follows a known response pattern to the study drug, but could have been produced by other factors such as the subject's clinical condition, intercurrent illness, or concomitant drugs. Information on drug withdrawal may be lacking or unclear.
- Probably related: The event or laboratory test abnormality follows a reasonable temporal sequence from the time of drug administration, and/or follows a known response pattern to the study drug, and unlikely to be explained by other factors such as the subject's clinical condition, intercurrent illness, or concomitant drugs. There is a positive response to drug withdrawal. Rechallenge is not required.
- Certainly related: The event or laboratory test abnormality follows a reasonable temporal sequence from the time of drug administration, and/or follows a known response pattern to the study drug, and cannot be reasonably explained by other factors such as the subject's clinical condition, intercurrent illness, or concomitant drugs. There is a positive response to drug withdrawal. Rechallenge is positive.

Adverse Events with a causality of “Possibly”, “Probably” or “Certainly” related meet criteria of ADRs.

All efforts should be made to classify the AE according to the above categories.

Action Taken

Action taken with study treatment due to the event which bases on the following categories:

- None (when no action is undertaken with the investigational product due to the event)
- Drug temporarily withdrawn

- Drug permanently withdrawn

Outcome of AE

Adverse events may result in one of the following outcomes:

- Death (only if the AE term reported is considered to be the cause of Death. Please note: for consistency, if outcome is ‘Death’ also seriousness must be ‘Death’)
- Recovered/resolved
- Recovered with sequelae
- Recovering/resolving
- Not Recovered/resolved: the event does not resolve

